The aim of this study is to perform a randomised controlled trial to study the changes in motor evoked potential amplitudes comparing sugammadex and placebo.

2. Background

Intraoperative monitoring (IONM) is most frequently employed in patients where the spinal cord or nerves are considered at risk. This may be evident through patient symptoms, pathological process or appearance on imaging.

Trained neurophysiologists that work in concert with the surgeon and anaesthesiologist perform the intraoperative monitoring. The monitoring commences once the patient has received general anaesthesia. Small electrodes are placed under the skin of the scalp and peripheries and different electrical stimuli are delivered to evoke a measured response. The neurophysiologist is able to monitor different potentials (motor evoked potentials, somatosensory evoked potentials, electromyography) and assess for a significant change.

Motor evoked potential monitoring is a well-established and safe intervention to assist in prevention of intraoperative injury during spine surgery.(Schwartz, Sestokas et al. 2011) There is no current consensus for criteria for change in amplitude for trans-cranial motor evoked potential monitoring. The peak-peak amplitude of the baseline motor evoked potential is utilised as a monitoring tool during surgery. The smaller the change in amplitude that is utilised as alarm criterion the more false positives that will be conveyed to the surgeons. (Legatt, Emerson 2016) Our neurophysiologists use a decrease in the amplitude by more than 50% or loss of the signal as a trigger to warn the surgeon of potential development of a neurological insult or injury.

The usual anaesthetic practice at our institution for patients undergoing posterior cervical spine surgery is to administer muscle relaxation to aid intubation at the start of the case and occasionally small doses of rocuronium (10-20mg) prior to turning the patient prone. The neuromuscular blockade is then allowed to wear off and the neurophysiologist will attempt to record their baseline motor evoked potentials during or just prior to surgical exposure.

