A peripheral nerve monitor may be used to monitor the degree of residual neuromuscular blockade. This is standard anaesthetic equipment with the most common mode to assess residual blockade used being a train of four count. This involves adhesive dots applied over the ulna nerve and a current applied (approximately 70-80mA) in a train of four impulses 0.5 seconds apart with a pulse width of 250 microseconds. It is a safe method of assessing the occupancy of

acetylcholine receptors at the neuromuscular junction by observing the number of twitches displayed in the peripheral muscle (e.g thumb movement).

Number of twitches

- 0- 100% receptors blocked
- 1- 90% receptors blocked
- 2- 75-80% receptors blocked
- 3- 75% receptors blocked
- 4- 0% receptors blocked

For the purposes of our study we plan to continuously monitor the train of four count and ratio using a peripheral nerve stimulator module that is built into the anesthesia machine (GE Datex Ohmeda). The train of four count on both measuring tools will be delivered as a train of four impulses 0.5 seconds apart (2Hz) at 70-80mA with a pulse width of 250 microseconds.

Our current approach does not involve routine measurement of the degree of residual neuromuscular blockade with a peripheral nerve stimulator. This is a safe approach as monitoring is achievable with partial blockade but may not necessarily be most beneficial in patients with existing neurological impairment as complete reversal of neuromuscular blockade is not ensured.(Li, Song et al. 2010)

The issues with this current technique are;

- a) Patients cannot be monitored for neurological changes during their transfer into the prone position
- b) There is likely residual neuromuscular blockade decreasing the amplitude of motor evoked potentials

A cases series of 10 patients in healthy subjects undergoing lumbar spine surgery demonstrated a 74% increase in mean amplitude of the MEPs with reversal of neuromuscular blockade with sugammadex 2mg/kg.(Batistaki, Papadopoulos et al. 2012)

We plan to perform a randomised controlled cross over trial comparing the change in MEP amplitudes with administration of sugammadex or placebo. This will be performed on at risk patients (e.g. cervical myelopathy) undergoing posterior cervical spine surgery where MEPs can be more difficult to attain but of higher utility.(Kombos, Kopetsch et al. 2003)

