6.1 Research Design

This is a prospective, single centre, triple blinded randomised controlled cross-over trial. Patients who are scheduled for an elective posterior cervical spine procedure in prone position and require motor evoked potential monitoring (MEPs) will be included. Patients will be randomised to assign to one of the following treatment sequences: sugammadex followed by placebo, or vice versa. The primary outcome is the change of MEP amplitude of the first dorsal interossei from baseline 3 minutes after administration of the allocated intervention. The patients, anesthesiologists and neurophysiologists (outcome assessor) will be blinded for the allocated intervention group.

The first study intervention will be performed after the patients are positioned in prone with a train of four count of 2 and satisfactory baseline motor evoked potentials have been recorded. This will likely occur during or just prior to surgical exposure.

The second study intervention will be performed during surgical closure. This will be once the surgeons have completed their use of motor evoked potentials and the patient remains on total intravenous anaesthesia (propofol and remifentanil). A minimum washout period of 100 min after the last bolus dose of rocuronium (equivalent to 5 half lives) is required and the completeness of washout will be confirmed with no residual tetanus fade, fade on train of four (or fading in double burst stimulation) on a peripheral nerve stimulator. The operative time

of posterior cervical spine procedure is usually around 3 hours and should allow complete washout of rocuronium. After the preconditions are achieved on peripheral nerve stimulator or the direct train of four monitor, the second intervention (either sugammadex or placebo) will be administered.

On each occasion the increase in amplitude of the motor evoked potential of both upper and lower limbs will be assessed at 3,6,9,12 and 15 minutes post intervention.

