8.2 Outcome Measurements

Primary Outcome Measure

The primary outcome measure is the increase in amplitude of the motor evoked potential measurements of the first dorsal interosseous muscle at 3 minutes following reversal of residual muscle relaxation with either sugammadex or placebo.

Secondary Outcome Measures

- Changes in the amplitude of the MEPs from the baseline in the first dorsal interosseous muscle at 6 and 9 minutes

- Side effects of reversal (hemodynamic changes, respiratory changes, surgeon observed patient movement, requirement for additional muscle relaxation and the anesthetic agents)
- Grading of relaxation of the surgical field by the surgeons using a four-point Likert scale (poor, acceptable, good and optimal) .

9. Data Collection and Management

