10.2 Sample size

A previous observational study reported sugammadex increased the amplitude of MEP by 74% (Batistaki, Papadopoulos et al. 2012). The normal upper limb MEP amplitude (first dorsal interosseus) is 2000 +/- 1600 microV from a previous published cross-over study in MEP (Chong, Manninen et al. 2014). Based on the assumption that the within-patient standard deviation of the MEP amplitude is 1600 microV and a power of 80%, a total of 30 patients is required in this two-intervention crossover study for detecting a treatment difference of 1200 microV (60% increment) at a two-sided 0.05 significance level. The sample size will be increased to 40 patients (20 patients per group) to cater for a potential 15-25% drop-out rate during the study.

11. Analysis

Statistical analysis will be performed using SPSS statistical software (version 14). The data distributions will be tested for normality with the Kolmogorov-Smirnov test. Descriptive statistics will be summarised as mean (\pm SD), median [Interquartile range (IQR)] or number (%) as indicated. The Mann-Whitney U test will be performed to compare the amplitude values of the two groups. TOF count, grades of surgical relaxation will be compared using the Chi-square test or Fisher's exact test according to the expected counts. In all cases, a P-value of 0.05 will be considered statistically significant.

12. Ethical aspects

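### The 1200 microV target equals a 60% rise only at a normal amplitude of 2000 microV, but the trial measures the rise from a partly blocked baseline, so the stated 80% power does not carry over to a 60% rise

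*Combined protocol and SAP*

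**What the plan says.** Section 10.2 takes its reference from a published crossover study: "The normal upper limb MEP amplitude (first dorsal interosseus) is 2000 +/- 1600 microV". It assumes that the "within-patient standard deviation of the MEP amplitude is 1600 microV and a power of 80" (per cent), and requires 30 patients for "detecting a treatment difference of 1200 microV (60% increment"), "at a two-sided 0.05 significance level". Enrolment is raised to 40 to allow for 15-25% drop-out. The only efficacy evidence cited is relative: a 74% rise in mean amplitude in a case series of 10.

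Section 6.1 defines the outcome against the trial's own baseline: "The primary outcome is the change of MEP amplitude of the first dorsal interossei from baseline 3 minutes after administration". Section 8.2 calls it "the increase in amplitude of the motor evoked potential measurements of the first dorsal interosseous muscle at 3 minutes". Neither section says whether the change is in microvolts, per cent or a log ratio.

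Section 7.2 has the baseline recorded at a train of four count of 2 or more. Section 2 (Background) equates a count of 2 with 75-80% of receptors blocked and, of current practice, says: "There is likely residual neuromuscular blockade decreasing the amplitude of motor evoked potentials". The alarm criterion given there is also relative: "Our neurophysiologists use a decrease in the amplitude by more than 50% or loss of the signal as a trigger".

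Section 11 plans a Mann-Whitney U test on the amplitude values of the two groups.

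**The concern.** The microvolt figure and the percentage in section 10.2 agree only when the starting amplitude is 2000 microV. The plan calls that value normal, yet it takes its baselines in a state that it says depresses the amplitude. The effect it has evidence for is proportional, so the same proportional effect from a lower start is a smaller number of microvolts. The power was calculated for the larger number.

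Two things are at stake. First, the 80% is the trial's only statement of what it can detect, and it may not describe a 60% rise as the trial will observe it. Second, a mean change in microvolts depends on the baseline amplitudes of the patients enrolled, and it is hard to carry over to patients with larger or smaller responses. The plan's effect estimate, target and alarm threshold are all expressed as proportions.

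**Working it through.** **Inputs.** From section 10.2: reference mean 2000 microV, within-patient SD 1600 microV, difference 1200 microV, two-sided alpha 0.05, power 80%, 30 evaluable patients, 40 enrolled. From sections 2 and 7.2: baseline taken under partial block. Not given anywhere: the amplitude or SD under block, or a within-patient log SD.

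**Step 1: reproduce the plan.** For a two-period crossover the total is N = 2 × [SD × (1.960 + 0.842) / difference]² = 2 × (1600 × 2.802 / 1200)² = 27.9, so 28 by the normal approximation. With the noncentral t distribution and SD of the paired difference = 1600 × √2 = 2263, N is 30 and power at 30 is 80%. Drop-out: 30/0.85 gives 36 and 30/0.75 gives 40. The stated 30 and 40 both reproduce. At the maximum planned drop-out, 40 enrolled leaves exactly 30.

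**Step 2: a 60% rise from a lower baseline.** Assume that 2000 microV is the fully reversed level. The blocked baseline is then 2000/1.6 = 1250 and the rise is 2000 − 1250 = 750 microV. From that baseline, 1200 microV would be a 1200/1250 = 96% rise. Power uses the paired t-test with SD of the difference = √(SD under sugammadex² + SD under placebo²), as in the plan's formula:

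| Assumed SDs (sugammadex, placebo) | SD of difference | Power, n = 30 | Power, n = 40 |
|---|---|---|---|
| 1600, 1600 (unchanged) | 2263 | 42% | 53% |
| 1600, 1000 (proportional to each arm's mean, CV 0.80) | 1887 | 56% | 69% |
| 1000, 1000 (both scale with the baseline) | 1414 | 80% | 90% |

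The last row matches the plan because 750/1414 = 1200/2263 = 0.53.

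Other assumed baselines with SD 1600 in both arms and a 60% rise, at 30 patients: 1500 microV gives a rise of 900 and 56% power; 1000 microV gives a rise of 600 and 29%.

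**Step 3: the same target as a ratio.** CV = 1600/2000 = 0.80. If the data are lognormal and this CV is within-patient, log SD = √ln(1 + 0.80²) = √ln 1.64 = 0.703. The target is ln 1.6 = 0.470 and the SD of the paired difference is 0.703 × √2 = 0.995. Power is about 71% at 30 and 83% at 40, and 80% needs 38 evaluable patients. At 30 patients, 80% needs a within-patient log SD of about 0.63 or less. For the 74% effect (ln 1.74 = 0.554), power at 30 is 84%.

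Step 3 keeps the plan's variance formula. If 0.703 instead applied independently to each single reading, the contrast of two changes from baseline would have SD 0.703 × 2 = 1.407, and power for a ratio of 1.6 would be 42% at 30 and 54% at 40. The restated calculation therefore has to say which quantity its SD describes.

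**Step 4: does the log scale gain power?** In simulated lognormal data (CV 0.80, 60% rise, 30 patients, change from baseline), a t-test on raw changes had about 65% power at within-patient correlation 0.5. Rank tests on raw changes and a t-test on log ratios each had about 70%. At correlation 0.7, rank tests had 89% and the log t-test 90%.

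**The case against.** The strongest reply is that the power loss is not demonstrated. No blocked amplitude is given, and the documents do not say that 2000 microV is the fully reversed level in these patients. If the SD falls with the baseline in both arms, power is the planned 80%. This stands as a limit on size. It does not restore the 80% as an established figure, because it needs an SD that follows the baseline down but does not grow when the amplitude rises by 60%. If the SD follows the mean in each arm, the figure is 56%.

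The plan also shaded its evidence down, from 74% to 60%; against 74% of 2000 (1480 microV), 1200 is the smaller figure. A reader might infer that the target is overstated outright. The documents do not support that, because it depends on the unknown baseline. But 1480 uses the same normal reference, so the mismatch remains.

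A reader might further infer that a log-ratio outcome recovers lost power. It does not: the plan already uses a rank test, rank tests on changes match the log analysis in simulation, and at the plan's own CV the log scale gives less than 80% at 30 patients.

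Strong skewness is likewise not reported. It is inferred from mean 2000 and SD 1600, where a normal curve would put 10.6% of values below zero. The plan does anticipate non-normal data, with a normality test, medians and a rank test.

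Finally, the planned Mann-Whitney test ignores the pairing of the crossover. Ranks of amplitude values do not change when logs are taken, so a log outcome alone would not repair this. That objection is right, and the fix must name a paired model.

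**Conclusion.** The concern holds as a mismatch between the target and the outcome. Section 10.2 equates 1200 microV with 60% at a reference that the plan's own account of residual block says its baselines fall below. A 60% rise from such a baseline is fewer than 1200 microV, and the stated 80% power is not established for it.

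The size cannot be fixed from the documents. Under the assumption that 2000 microV is the reversed level, power at 30 patients runs from 42% to 80%, and at 40 from 53% to 90%. It should not be reported as a single shortfall. These figures treat the two periods' errors as independent and 1600 as within-patient, as the plan does.

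A further limit is that the degree of block at baseline may vary. Section 2 equates a count of 4 with no receptors blocked, and section 7.2 admits any count of 2 or more. For the second period, sections 6.1 and 7.2 require the absence of fade, while the crossover paragraph of 7.2 makes further relaxant conditional on need. These passages must be reconciled; a ratio outcome does not settle them.

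**What to change.** - **Section 10.2:** state the target as a ratio of 1.6 between the 3-minute amplitude and the same-period baseline. Drop 1200 microV, or label it as holding only at a 2000 microV baseline. Justify a within-patient log SD, say whether it refers to single readings or to changes, and state the power at 30 and at 40 patients.
- **Sections 6.1 and 8.2:** define the primary outcome as log(3-minute amplitude / same-period baseline amplitude).
- **Section 11:** replace the unpaired Mann-Whitney test for the primary outcome with a paired crossover model on that log ratio, with treatment, period and sequence. Report the sugammadex:placebo ratio with its 95% CI.
- **Near-zero responses:** pre-set a recording floor and add a sensitivity analysis to it, because very small values can dominate a log analysis.

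The cost is wording and one recalculation, with no new data. The downsides are that a floor has to be chosen and that the restated power may be less favourable than 80%. The benefit is a target and an estimate that do not rest on the 2000 microV reference.

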The crossover arm of the trial is to enable patients to function as their own control group. During surgical closure patient will remain on a total intravenous anaesthesia (propofol and remifentanil). When the patient returns to a train of four count of 2 or more on peripheral nerve monitor repeat motor evoked potentials will then be recorded and

patients will receive the alternate drug to the one received in the initial arm of the trial.

The purpose of this study is to determine the increase in amplitude of the motor evoked potentials when residual neuromuscular blockade is reversed with sugammadex or placebo.

4. Hypothesis

We hypothesize that reversal of neuromuscular blockade by sugammadex will increase the amplitude of motor evoked potentials compared with placebo.

5. Significance of the study

Facilitating increased amplitudes of MEPS via reversal of residual neuromuscular blockade will enable increased accuracy of monitoring.

Providing the option of reversal of neuromuscular blockade will allow MEPs to be monitored during patient positioning to prevent placing them in a neurologically compromising position.

6. Methods

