10.1 Hypotheses

Null Hypothesis- There is no difference between the amplitude of the baseline motor evoked potentials before and after reversal with sugammadex or placebo.

Alternative Hypothesis- There is a difference in the amplitude of the baseline motor evoked potentials before and after reversal with sugammadex or placebo.

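### The only test named for MEP amplitude is for two independent samples, although the trial is a crossover sized on a within-patient SD, so the stated 80% power is not assured

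*Combined protocol and SAP*

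**What the plan says.** The design is a two-sequence, two-period crossover. Section 6.1 states: "Patients will be randomised to assign to one of the following treatment sequences: sugammadex followed by placebo, or vice versa". The background text before Section 4 gives the reason: "The crossover arm of the trial is to enable patients to function as their own control group". Section 6.1 defines the endpoint: "The primary outcome is the change of MEP amplitude of the first dorsal interossei from baseline 3 minutes after administration of the allocated intervention".

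Section 10.2 sizes the trial on within-patient variation: "Based on the assumption that the within-patient standard deviation of the MEP amplitude is 1600 microV and a power of 80" per cent. This gives 30 patients for a difference of 1200 microV at two-sided 0.05. Enrolment is then raised to allow for 15–25% drop-out: "The sample size will be increased to 40 patients (20 patients per group").

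For amplitude, Section 11 names one test: "The Mann-Whitney U test will be performed to compare the amplitude values of the two groups". The other procedures there are Kolmogorov-Smirnov for normality and chi-square or Fisher's exact test for train-of-four count and relaxation grade. No section gives a paired test, a crossover ANOVA, a mixed model, a within-patient difference or a period term.

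**The concern.** The Mann-Whitney U test assumes two independent samples. Here each patient contributes a value under both treatments, so the test as worded ignores the pairing on which the sample size rests. It also ignores period.

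Three further gaps leave the primary analysis undetermined:

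- The endpoint is a change from baseline, but the test is applied to amplitude values.
- The two groups are not defined. Section 10.2 uses the word group for the randomised sequences. On that reading each comparison uses one period only, and half of each patient's data is left out.
- Section 10.1 words the null as before versus after: "There is no difference between the amplitude of the baseline motor evoked potentials before and after reversal with sugammadex or placebo". Section 4 makes it a comparison of treatments: "We hypothesize that reversal of neuromuscular blockade by sugammadex will increase the amplitude of motor evoked potentials compared with placebo".

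Two things are at stake. The test may miss an effect that the paired design would detect. And several different comparisons fit the wording, so the choice could be made after the data are seen. Nor does the plan provide for a treatment-effect estimate with a confidence interval.

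**Working it through.** **Inputs.** From Section 10.2: difference 1200 microV, within-patient SD σw = 1600 microV, two-sided 0.05, power 80%, 30 evaluable, 40 enrolled, drop-out 15–25%. From Section 6.4: 1:1 allocation. Completers are 40 × 0.75 = 30 or 40 × 0.85 = 34. The correlation ρ between a patient's two raw amplitudes is not in the documents. I assume 0.25 to 0.5 and show 0 to 0.7 as the outer range.

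**Step 1: reproduce the plan's figure.** In a crossover the variance of the treatment difference is 2σw²/N, so

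N = 2 × [1600 × (1.960 + 0.842) / 1200]² = 2 × 3.736² ≈ 27.9, i.e. 28.

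The noncentral t version with N − 2 df gives power 0.8006 at N = 30, so 30 is reproduced. Then 30 / (1 − 0.25) = 40, as stated. If 1600 were the SD of the paired difference, N would be 16, so that is not what was done. The sample size is sound for a paired analysis.

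**Step 2: what ignoring the pairing does.** With within-patient SD 1600 the total SD is 1600/√(1 − ρ): 1848 at ρ = 0.25 and 2263 at ρ = 0.5. The true standard error at N = 30 is still 1600 × √(2/30) = 413, and 1200/413 = 2.905. An unpaired test works from the total SD, so its critical value is in effect raised from 1.960 to 1.960/√(1 − ρ).

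- ρ = 0.25: 1.960/√0.75 = 2.263; power Φ(2.905 − 2.263) ≈ 0.74; true type I error about 0.024.
- ρ = 0.5: 1.960/√0.5 = 2.772; power Φ(2.905 − 2.772) ≈ 0.55; true type I error about 0.006.

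**Step 3: the rank test itself.** Simulation with normal errors, 10,000 trials per setting, σw = 1600, raw amplitudes pooled by treatment:

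| ρ | Mann-Whitney power, N = 30 | Type I error, N = 30 | Mann-Whitney power, N = 34 |
|---|---|---|---|
| 0 | 0.788 | 0.049 | 0.841 |
| 0.25 | 0.694 | 0.023 | 0.759 |
| 0.5 | 0.510 | 0.008 | 0.573 |

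The paired t-test has 0.80 at N = 30 and 0.85 at N = 34. A separate run of 5,000 trials extended this to ρ = 0.7, where power at N = 30 is 0.23. With no drop-out at all (N = 40) it gives 0.89, 0.80, 0.67 and 0.37 at ρ = 0, 0.3, 0.5 and 0.7.

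**Step 4: the other readings of Section 11.**

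- *1600 as total SD, pooled raw amplitudes, N = 30.* Mann-Whitney power is 0.796, 0.824, 0.865 and 0.915 at ρ = 0, 0.25, 0.5 and 0.7, against 0.805, 0.900, 0.978 and 0.999 for paired t. This is adequate but less efficient.
- *Groups as sequences, one period only.* With total SD 1600, power is about 46–48% at 15 v 15 and 54% at 17 v 17, with valid type I error. With 1600 as within-patient SD it falls at 15 v 15 to 0.35 at ρ = 0.3 and 0.27 at ρ = 0.5.
- *Change scores with independent baseline error.* Subtracting the baseline removes the patient component, so there is nothing left for pairing to remove. Type I error is about 0.05 and power is within 2 points of a paired t-test on the same scores. Both are near 50% at N = 30. As a check, the SD of a difference of two changes is 2 × 1600 = 3200; 1200/(3200/√30) = 2.05; Φ(2.05 − 1.96) ≈ 0.54.

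**The case against.** The strongest reply is that the power loss in Step 3 is not shown for the declared endpoint, which is a change from baseline. If amplitude values is shorthand for change scores, ignoring the pairing costs almost nothing. This stands, and the 51–69% figures are claimed for raw amplitudes only. But it does not rescue the 80%: on simple change scores either test has about 50%, because of baseline noise that the sizing does not include.

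Second, Section 10.2 quotes the source as 2000 ± 1600 microV, so 1600 may be a total SD, and the pooled test then has 80–92%. This also stands, and it is why the conclusion is that the power is not assured, rather than that it is lost. The plan itself calls 1600 within-patient.

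Third, the simulations use normal errors, although a mean of 2000 with an SD of 1600 suggests skew. In a lognormal check (total SD 1600, ρ = 0.25, 60% multiplicative effect, N = 30) the pooled Mann-Whitney had 0.72, paired t 0.70 and a within-patient regression 0.68. At ρ of 0.5 or more, pairing wins. So the advantage of pairing depends on scale as well as correlation.

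Fourth, all figures assume the same effect in both periods. Section 6.1 requires no residual fade before the second intervention. Section 7.2 gives further rocuronium only if needed, yet doses at a train-of-four count of 2 or more. If the second-period effect were nil, an extreme case, the regression proposed below would have about 28% power. Those passages must be reconciled, but that is a separate point and does not justify an independent-samples test.

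Finally, a Mann-Whitney test on within-patient period differences is a valid crossover method. Section 11, however, mentions no differences.

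**Conclusion.** The concern holds and should be corrected before any data are analysed. The sole test named for the primary outcome does not fit the crossover design, the endpoint or the calculation behind the 80% power.

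If 1600 microV is the within-patient SD and raw amplitudes are pooled by treatment, power at 30 completers is about 69% to 51% for assumed correlations of 0.25 to 0.5. The loss is about 1 point at zero correlation. If 1600 is the total SD there is no shortfall on the pooled reading, but the one-period reading stays near 47%. Type I error is nominal or below it on every reading examined, so the harm is a missed effect and an analysis left open, not a false positive.

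**What to change.** In Section 11, replace the Mann-Whitney sentence with a within-patient crossover comparison of sugammadex and placebo for the 3-minute first dorsal interosseous outcome. One choice is a mixed model with treatment and period, the same-period baseline as covariate and patient as random effect, reporting the treatment difference with a 95% CI. A within-patient version regresses the period difference on sequence and baseline difference. In 6,000 simulated trials per setting (σw = 1600) that regression had 78–79% power at 30 completers and 83–85% at 34, with type I error about 0.05. These figures belong to the regression; the mixed model was not simulated.

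If a rank test is preferred, apply Mann-Whitney to the within-patient period differences, compared between sequences. On 3-minute amplitude this has about 76–77% power at 30 and 83–84% at 34. Both options fall slightly short of 80% at the full 25% drop-out.

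Use the same analysis at 6 and 9 minutes. A log scale is optional, but given the likely skew the choice should be fixed in advance. Restate the null in Section 10.1 as no difference between sugammadex and placebo in the change in MEP amplitude, to match Section 4.

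The cost is rewording of Sections 10.1 and 11. No extra patients or measurements are needed.

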7.2 Study Protocol

Patients should undergo peripheral nerve monitoring following the induction via a peripheral nerve stimulator and by a direct train of four monitor by the neurophysiologists. The train of four should be assessed on peripheral nerve stimulator and on the neurophysiology monitoring prior to turning the patient prone. If the patient has two or more twitches on either monitoring they should be given 0.1mg/kg rocuronium prior to positioning prone.

Once the patient is in their final position for surgery the anaesthetic will be changed to a total intravenous anaesthetic (TIVA) with propofol and remifentanil titrated to entropy of 40-60. The volatile anaesthesia has to be washed out with high flows of 10L/min until end tidal desflurane is less than or equal to 0.2.

When the above conditions are met the train of four count (TOFC) will be checked by the anaesthesiologist. When the TOFC is 2 or more the baseline motor evoked potentials (bMEPs) will be performed.

Following the bMEPs the anaesthesiologist will administer the reversal drug (either sugammadex 2mg/kg in 10 ml syringe or matching placebo). This time must be strictly recorded, as it is the time that has elapsed since the induction dose of muscle relaxant. The neurophysiologist will perform and record MEPS at 3,6 and 9 minutes post reversal dose. The following parameters will continuously be monitored during the study period: TOFC, Entropy, BP, HR, CO2,

peak airway pressures, anaesthetic infusion rates, temperature and oxygen saturation. If the testing occurs during surgical exposure it is important to ask the surgeons to make a very brief pause to allow the motor testing to be performed and to check the entropy at the same time.

Following surgery commencement there will be a surgical grading of the relaxation of the surgical field once exposure attained and collection of surgeon stated observation of patient movement.

The operative time of posterior cervical spine procedure is usually around 3 hours and should allow for complete washout of rocuronium. A minimum washout period of 100 min after the last bolus dose of rocuronium (equivalent to 5 half-lives) is required and the completeness of washout will be confirmed with no residual tetanus fade, no fade on train of four (or fading in double burst stimulation) on a peripheral nerve stimulator.

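### The surgical relaxation grade has four ordered levels, but the planned chi-square or Fisher test ignores the order and loses power against a one-directional shift

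*Combined protocol and SAP*

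**What the plan says.** Section 8.2 lists, under "Secondary Outcome Measures", this item: "Grading of relaxation of the surgical field by the surgeons using a four-point Likert scale (poor, acceptable, good and optimal". The four labels form an ordered scale.

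Section 7.2 describes one grading: "there will be a surgical grading of the relaxation of the surgical field once exposure attained". Section 6.1 says of the first study drug: "This will likely occur during or just prior to surgical exposure". Section 7.2 also allows for dosing part-way through exposure: "If the testing occurs during surgical exposure it is important to ask the surgeons to make a very brief pause".

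Section 11 gives the analysis: "TOF count, grades of surgical relaxation will be compared using the Chi-square test", or Fisher's exact test, with the choice resting on the expected cell counts. It does not name the groups being compared, and it gives no threshold for choosing between the two tests. The same section plans a Mann-Whitney U test, but only for MEP amplitude.

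On numbers, section 10.2 says "The sample size will be increased to 40 patients (20 patients per group", with 30 required before the allowance for drop-out. No power or effect size is given for the grade.

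**The concern.** Chi-square and Fisher return the same p-value however the four labels are shuffled. They spread their sensitivity over every kind of difference between two sets of four proportions. The natural worry here has a direction: less blockade may mean a less relaxed field. The grade is the listed outcome that records surgical conditions after reversal. A test blind to direction is more likely to miss a real worsening and leave a non-significant result that reads as reassurance. Neither test gives an effect estimate with an interval, so a reader could not see how much worsening remains compatible with the data.

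**Working it through.** **Which comparison.** Only one grading is described, at exposure, soon after the first study drug. The natural contrast is therefore between the two first-intervention groups, unpaired, about 20 v 20. This is inferred, because section 11 does not say so.

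**Which planned test applies.** A 2 x 4 table has 8 cells, so 40 patients give 40/8 = 5 expected per cell on average, and any unevenness puts some cells below 5. The assumed rule was Fisher (Freeman-Halton) if more than 20% of expected counts are below 5 or any is below 1, otherwise Pearson chi-square. Fisher was then used in 96-100% of simulated tables.

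**The plan's own figures.** There is none for the grade. The group sizes used here follow section 10.2: 30/(1 - 0.25) = 40, so 20 per group randomised, and 15 per group if only the required 30 remain.

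**One invented table**, poor to optimal: 1/4/8/7 v 4/8/5/3, with 20 per group.
- Column totals are 5, 12, 13, 10, so the expected counts per group are 2.5, 6, 6.5, 5.
- Chi-square = 2 x (1.5²/2.5 + 2²/6 + 1.5²/6.5 + 2²/5) = 5.43 on 3 df, p = 0.143.
- Two of the 8 expected counts (25%) are below 5, so the rule selects Fisher: p = 0.185.
- Mann-Whitney: the midranks are 3, 11.5, 24, 35.5. The first group's rank sum is 3 + 46 + 192 + 248.5 = 489.5, against an expected 20 x 41/2 = 410. The tie-corrected variance is (400/12) x (41 - 5010/1560) = 1259.6. So z = 79.5/35.49 = 2.24, p = 0.025.

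The same data fall on opposite sides of 0.05.

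**Simulated power.** 6000 trials per setting, two-sided 0.05. The shift is proportional-odds toward worse grades: each cumulative odds is multiplied by the odds ratio (OR). For example, 25/25/25/25% becomes 50/25/15/10% at OR 3. Assumed reference grades (poor/acceptable/good/optimal, %):
- spread out: 25/25/25/25, 10/40/35/15, 5/20/40/35, 5/15/30/50;
- concentrated: 1/4/20/75, 0/5/15/80, 1/2/7/90, 2/8/80/10.

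Power at 20 v 20, planned rule v tie-corrected Mann-Whitney (normal approximation):

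| OR | Spread out | Concentrated | Gain, both sets (points) |
|---|---|---|---|
| 1.5 | 7-8% v 10-11% | 3-7% v 6-9% | 2-3 |
| 2 | 13-14% v 21-22% | 6-12% v 10-17% | 4-8 |
| 3 | 29-31% v 44-47% | 15-29% v 23-39% | 8-16 |
| 4 | 45-47% v 64-65% | 25-42% v 38-56% | 13-20 |

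At 15 v 15, over both sets: OR 2, 3-12% v 7-18%; OR 3, 9-23% v 17-37%; OR 4, 17-35% v 28-52%.

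Type I error at 20 v 20 is 1.7-4.7% for the planned rule and 3.9-5.3% for Mann-Whitney.

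**How much is due to order.** Where grades are concentrated, Fisher runs well below 5%, so part of the gain is recovered conservatism. Against an exact conditional rank test (4000 trials, type I error 1.1-4.8%), the gains at OR 2, 3 and 4 are 6-8, 13-15 and 17-18 points with spread-out grades. With concentrated grades they are only about 0-2, 2-7 and 5-10 points. For 1/2/7/90 at OR 2 there is no gain (6.4% planned v 6.0% exact rank).

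**Second simulation.** A separate run of 4000 trials on three spread-out baselines gave 28-30% v 44-47% at OR 3 and 46-47% v 65% at OR 4. A linear-by-linear trend test was within about 1.5 points of Mann-Whitney.

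**Where the rank test loses.** Symmetric spread to both extremes, 20 v 20, planned rule v Mann-Whitney:
- 10/40/40/10 v 30/20/20/30: 57% v 6%.
- 15/35/35/15 v 35/15/15/35: 55% v 6%.
- 5/45/45/5 v 30/20/20/30: 85% v 6%.

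**The case against.** This is a choice between valid tests for the last-listed secondary outcome, which has no power target, while the hypotheses in section 10.1 concern amplitude only. No error rate is inflated. Every power figure rests on assumed distributions and odds ratios, and at OR 2 or 3 the outcome is underpowered under either test. If most patients share one grade, an exact rank test gains little. A rank test is also nearly blind to a symmetric spread. The groups are inferred; if the grade were also taken at closure, the data would be paired and an unpaired test would not fit. Train-of-four count, in the same sentence, is ordered too.

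Most of this stands and limits the weight of the point. None of it gives a reason to discard the order. A shift in one direction is the more plausible effect of reversal, and the normal-approximation rank test was ahead in every setting with OR above 1. Only one grading is described, so the unpaired reading is the reasonable one. A symmetric spread would show in the tabulated counts. The principle does extend to train-of-four count, but that comparison was not worked through here and no change to it is proposed.

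**Conclusion.** The concern holds, as a minor loss of efficiency and not of validity. With spread-out grades at 20 v 20, the planned rule gives up roughly 7-8 points of power at OR 2, 13-16 at OR 3 and 17-20 at OR 4. With concentrated grades the loss is smaller and due partly to Fisher's conservatism.

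This rests on assumed grade distributions, a proportional-odds shift, an assumed threshold for switching to Fisher, and one grading compared between first-intervention groups. If the drug is given part-way through exposure, the grade partly reflects earlier relaxation, so the true shift and the gain may sit at the low end. The primary analysis and the sample size do not change.

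**What to change.** In section 11, state that the relaxation grade is compared between the two first-intervention groups with a tie-corrected Mann-Whitney test or a proportional-odds model. Report the common odds ratio with its 95% CI, and tabulate the four grade counts by group so that a non-monotone pattern would be seen. If grades are too concentrated for the odds ratio to be estimated, report the rank test and the counts. Confirm that the grade is taken once; a second grading at closure would need a paired ordinal method. No view is taken here on Mann-Whitney for the crossover amplitude analysis.

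The cost is one or two sentences and no extra data. The price is little power against a symmetric spread to both extremes, which the tabulated counts would reveal.
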